The proposed study will use parallel-groups, randomized, sham controlled, double-blinded design in which 36 participants with motor incomplete SCI (AIS B – D level) will randomly assigned to receive tDCS combined with repetitive arm training (RAT) or sham tDCS combined with R-A training. During the first 20-minute participants (n=24) in the experimental group will receive 20 minutes of anodal tDCS (2 mA) on motor cortex contralateral to their trained side followed by RAT for 60 minutes. Participants (n=12) in the control group will receive 20 minutes of sham tDCS followed by RAT for 60 minutes. In the sham stimulation 2 mA of anodal current will be delivered in a ramp up and down fashion for 30 seconds at the beginning and 30 seconds at the end of 20 minutes of stimulation. Treatment will be administered at an intensity of 5 sessions per week for 2 weeks.

The randomization schedule will be provided by project statistician ([name]).

Outcome measure:

Feasibility outcome measure: Adherence with therapy will be measured as;
(1) the number of treatment sessions attended by each participant,
(2) number of drop-outs in each group,
(3) participant's perceptions of the use of study implementation (using the tDCS and exercise equipment, numerical rating scale with 'not difficult at all' at 0, and 'very difficult' at 10)
(4) participant's perceptions of usefulness of the intervention (numerical rating scale with 'not at all useful' at 0 and 'very useful' at 10).

The telerehabilitation intervention will be considered as feasible if at least 80% adherence rate is achieved (completed number of sessions \geq 8 out of 10), if attrition rate is no higher than 10% in each study group, if at least 40 minutes of 60 minutes exercise session is completed and if no serious adverse events took place (other than expected side effects from tDCS).

Clinical outcome measure: Primary clinical outcome measure is GRASSP prehension performance (Kalsi-Ryan et al., 2012). Secondary clinical outcome measures are grip strength and Spinal Cord Injury Independence Measure (SCIM III) (Itzkovich, Gelernter et al. 2007). Assessments will be repeated immediately after completion of 10 sessions and at 4-weeks follow-up.

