- (3) any joint contracture or severe spasticity in the affected upper extremity, as measured by a Modified Ashworth Score \geq than 3 out of 4.

6. Study Procedures:

Baseline Assessment (Duration: two to three hours): For both SCI subjects and healthy volunteers, the baseline assessment can be on the same visit as screening and will be performed in the Motor Recovery Laboratory by an evaluator blinded to subject's group assignment. Subjects (SCI) will be evaluated for upper extremity motor functions. Arm and hand functions will be assessed with Graded Redefined Assessment of Strength, Sensibility and Prehension (GRASSP), ASIA upper extremity scale (motor and sensory), grasp and release test and independence in daily functions will be assessed with SCIM-II.

Caregiver training: On the day of in-clinic baseline assessment, caregiver/family member who will be delivering the therapy at home will be trained on intervention protocol (localization of primary motor cortex to deliver the tDCS, operating the tDCS machine, operating the laptop and videoconference system, using special exercise equipment). Then they will take the tDCS device, exercise equipment and lap top computer home.

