Data for feasibility and adherence will be analyzed using descriptive statistics. For effectiveness, difference in GRASSP score in active arm and between active vs sham arm (immediately after treatment - baseline) will be analyzed with paired t test (if the normality is satisfactory with Kolmogrov-Smirnov test). If the K-S test suggests skewed distribution, we will conduct Wilcoxon signed rank test and Wilcoxon rank sum test for these two analyses.

In multivariable analysis, we will fit a mixed model for data collected at baseline and ten sessions and at 30-days follow-up in both study arms. Patient will be included as random effect of the mixed model. The fixed effects include treatment arm (active, sham) and time (0 for baseline, 1-10 for ten sessions). First, we will consider time levels as nominal and test interaction between treatment and time. The interaction will be added if it will be significant. Second, we hope to parametrically model time. The mean trajectory plot will guide us on the parametric form of time. Our emphasis will be linear time and 3rd-order polynomial time. We tend to favor the 3rd-order polynomial time as we believe that the GRASSP score will increase greatly for the first few sessions and then become stable.

In mixed model analysis, besides incorporating patient random effect, we will also test if there exists stronger correlation among measurements with shorter time intervals. We will specify a few serial correlation patterns including exponential, Toeplitz and banded Toeplitz. The random effect specification will be extended to incorporate random time slope. We will fit all these models and report AIC values to guide our decision on covariance pattern.

10. Potential Benefits

The results of these studies may benefit subsequent future subjects if remotely supervised, home-based combined tDCS and repetitive arm training proves to be effective when compared to repetitive arm training only.

The benefits of participating in this study may be improved arm and hand movement. However, there may be no benefit from participating in this study.

11. Risk-Benefit Ratio:

The potential improvement of arm and hand movement outweighs the risk of non-invasive brain stimulation, fatigue, pain and discomfort.

12. Consent Procedures:

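### The between-arm GRASSP comparison uses raw change with no baseline covariate; ANCOVA on the baseline already collected removes the effect of chance imbalance at almost no cost

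*Combined protocol and SAP*

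**What the plan says.** Section 4 (Study Design) has "36 participants with motor incomplete SCI (AIS B – D level) will randomly assigned", split unequally: "participants (n=24) in the experimental group will receive 20 minutes of anodal tDCS" and "Participants (n=12) in the control group will receive 20 minutes of sham tDCS". It says that the statistician supplies the randomisation schedule, but mentions no stratification or balancing on GRASSP or AIS grade. On the outcome it states: "Primary clinical outcome measure is GRASSP prehension performance".

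Section 6 (Study Procedures) collects this outcome at the baseline visit: "Arm and hand functions will be assessed with Graded Redefined Assessment of Strength, Sensibility and Prehension (GRASSP"). The schedule of activities marks GRASSP at baseline, post-treatment and follow-up.

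Section 9 (Data analysis) then takes the "difference in GRASSP score in active arm and between active vs sham arm (immediately after treatment - baseline") and names a paired t test for it. For skewed data it substitutes signed rank and rank sum tests. For the mixed model it says: "The fixed effects include treatment arm (active, sham) and time (0 for baseline, 1-10 for ten sessions"). The arm-by-time interaction enters only if it is significant. Baseline GRASSP is a covariate in none of these analyses.

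**The concern.** Subtracting baseline fully removes a chance difference between the arms only if the regression slope of post on baseline is 1. If the slope is below 1, the arm that happens to start lower appears to gain more. If it is above 1, the arm that starts higher does. With 24 and 12 people spread over AIS B to D and no stated balancing, some baseline gap is likely in any one trial. At stake are how far the single tDCS estimate can be trusted once a gap has appeared, and whatever precision the baseline measurement could add. This is separate from the naming of a paired test for independent arms: a correct two-sample test on the same change scores would leave the point unchanged.

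**Working it through.** **Plan's own figure.** The total of 36 cannot be reproduced, because the documents give no effect size, SD, alpha or power.

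**Inputs.** From Section 4: n = 24 and 12. Assumed: two-sided alpha 0.05; SD of 1 at both visits (results are in baseline SDs); baseline-to-post correlation rho of 0.5, 0.7 or 0.9.

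**Size of a chance gap.** SD of the baseline mean difference = sqrt(1/24 + 1/12) = sqrt(0.125) = 0.354. P(|gap| ≥ 0.5) = P(|Z| ≥ 0.5/0.354 = 1.414) = 0.157.

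**Shift given the gap.** The change-score estimate moves by −(1 − rho) × gap. Its standard error is sqrt(2(1 − rho)) × 0.354.

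**Precision.** The variance factor is 2(1 − rho) for change and 1 − rho² for ANCOVA, so the ratio is (1 + rho)/2. Estimating the slope at N = 36 multiplies this by 1 + 1/(36 − 4) = 1.031.

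| | rho 0.5 | rho 0.7 | rho 0.9 |
|---|---|---|---|
| Size of shift for a 0.5 SD gap (SD) | 0.25 | 0.15 | 0.05 |
| Shift in SEs of the change estimate | 0.71 | 0.55 | 0.32 |
| Variance ratio, no penalty | 0.75 | 0.85 | 0.95 |
| Variance ratio with penalty | 0.77 | 0.88 | 0.98 |
| Change-score N for equal precision (36/ratio) | 47 | 41 | 37 |
| ANCOVA power where the change test has 80% | 88.9% | 84.8% | 80.7% |

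The power row takes the effect at which the change-score t test reaches 80% power (1.02 SD of change) and uses the noncentral t with 33 degrees of freedom for ANCOVA.

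**Break-even.** (1 + rho)/2 × 33/32 = 1 gives rho = 64/33 − 1 = 0.94.

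**Simulation under no effect.** The slope of the change-score estimate on the gap was about −0.50, −0.30 and −0.10; for ANCOVA it was about 0. Overall type I error of the change-score test was about 5% throughout. Among trials in which the active arm started at least 0.5 SD lower, the test wrongly favoured active in about 12%, 9% and 6%, against a nominal 2.5%.

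**Unequal SDs.** With k = SDpost/SDpre, the slope of change on baseline is rho × k − 1. At rho 0.8 and k = 1.25 it is 0.8 × 1.25 − 1 = 0. The change variance is then 1 + 1.5625 − 2(0.8)(1.25) = 0.5625 and the ANCOVA variance is 1.5625 × 0.36 = 0.5625, so nothing is gained and only the 3% penalty remains. For larger k the slope is positive and the shift reverses direction.

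**Mixed model.** With the interaction, time as nominal and complete data, the post-minus-baseline arm contrast is the same unadjusted change difference. Without the interaction, the arm effect averages over baseline as well. With three equally correlated GRASSP visits, the gap enters with weight (1 + 2 rho)/3 = 0.67, 0.80 and 0.93, and it favours the arm that starts higher. Neither form adjusts for baseline.

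**The case against.** The strongest reply is that randomisation already makes the change-score comparison valid, and that the gain here may be very small. Both parts largely stand.

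- A reader might infer that the planned test is biased or has an inflated false-positive rate. It does not: averaged over randomisations the estimate is unbiased and type I error is about 5%. The shift is conditional on the gap that occurs.
- A reader might infer that the lower-starting arm always appears to gain more. That requires rho × SDpost/SDpre below 1, and the documents give none of these quantities.
- A reader might infer a material loss of power. Section 5 recruits people with chronic injury whose arm therapy is to stay stable, treatment lasts two weeks, and the AIS B to D range widens between-person spread. All of this points to a high correlation. At 0.9 the variance saving is about 2%, and above about 0.94 ANCOVA is marginally worse.
- No stated power is contradicted, because none is stated, and the first aim is feasibility.

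What remains is that the plan has no protection against an observed gap beyond subtraction, although the means of adjustment is already in the data. At high correlation adjusting costs almost nothing; at moderate correlation it is worth several participants.

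**Conclusion.** The point holds as one of conditional imbalance and efficiency. The planned estimate moves by (1 − rho) times any chance baseline gap: 0.25, 0.15 or 0.05 SD for a 0.5 SD gap at rho 0.5, 0.7 or 0.9. A gap of that size or more arises in about 16% of trials with 24 and 12 participants. ANCOVA removes the shift and has about 0.77, 0.88 or 0.98 of the variance. These figures rest on equal SDs at the two visits and an assumed range for rho. The allocation, the absence of a covariate and the availability of baseline GRASSP come from the documents. The documents do not support calling the planned test invalid, or claiming a large loss of precision. The change is worth making because it is nearly free.

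**What to change.** In Section 9, make the primary between-arm analysis an ANCOVA of post-treatment GRASSP prehension performance on arm plus baseline prehension performance, reported as an adjusted difference with 95% CI. Check the residuals of that model. If they are clearly non-normal, use a baseline-adjusted rank ANCOVA or a permutation ANCOVA in place of the unadjusted rank sum test, with the criterion written down in advance. Use the same model for GRASSP at the 4-week visit and for SCIM. Extend it to grip strength only once its baseline measurement is confirmed: its row in the schedule of activities has no marks, and the baseline assessment in Section 6 does not list it, although the post-treatment paragraph speaks of repeating it.

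The cost is a few sentences, settled before unblinding, and one degree of freedom (34 to 33). GRASSP and SCIM need no new data.

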Schedule of activities

Event	Baseline (Day -6 to 0)	Treatment Sessions (1-10)	Post-treatment (Day 5±3)	Follow-up 1 (Day 35±5)
Informed Consent	X			
Inclusion/Exclusion Criteria	X			
Demographics	X			
Medical and Social History	X			
Medication Checklist	X		X	X
ASIA-Impairment Scale	X		X	X
GRASSP	X		X	X
Grip Strength				
NHPT	X		X	X
SCIM-II	X		X	X
tDCS	X			
Music Glove and FitMi arm training		1-10		
tDCS-Side Effects Questionnaire		1-10		
Pain and Fatigue		1-10		
Participant-tDCS &Arm Exercise Survey		1,6,10		
Participant- Usefulness of Intervention Survey			X	X
Caregiver tDCS&Arm Exercise Survey		1,6,10		
Caregiver-Usefulness of Intervention Survey			X	X

Post-treatment and Follow-Up Assessment (Duration: two-hours): During this period subjects will be asked to come within a-week after they have completed the study and at week 4 for follow-up. GRASSP, Grip Strength, SCIM-II and fNIRS measurements will be repeated at post-treatment visit and at 4-week follow-up visit.

7. Potential Risks/Discomforts

tDCS: Transcranial direct current stimulation (tDCS) is a technique that poses a non-significant risk to subjects. The safety of this technique has been addressed and tested by multiple researchers (e.g., Hummel, et al., (Hummel and Cohen, 2005); Fregni, et. al., (Fregni et al., 2006a, Iyer et al., 2005); Nitsche, et al., (Nitsche et al., 2003c, Nitsche et al., 2003b, Nitsche et al., 2003a), (Nitsche et al., 2004); Priori, et al., (Priori, 2003)). Researchers have concluded that tDCS, as applied in a manner similar to our proposed protocol, induces only temporary mood, cognitive / motor effects, and no negative side effects. No undesirable or long-lasting effects have been reported, nor have any subjects reportedly abandoned a study due to discomfort. The most common side effects according to a recent consensus are: headache, dizziness, nausea, itchy sensation as well as irritation under the area of the electrodes (Nitsche et al., 2008). Researchers at the National Institute of Neurological Disorders and Stroke (NINDS), Iyer et al., (2005) (Iyer et al., 2005) conducted a safety study on tDCS, investigating 20-minute sessions of 1 mA and 2 mA current stimulation with healthy controls (n=103). No negative effects were identified. Nitsche and colleagues (2004) found no measurable structural changes in brain tissue due to tDCS (Nitsche et al., 2004). Finally, two recent studies showed that

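### The active-versus-sham GRASSP comparison is assigned a paired t test that cannot be run on independent arms of 24 and 12, and no between-arm analysis is named primary

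*Combined protocol and SAP*

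**What the plan says.** Section 4 (Study Design) sets out a parallel-group, randomized, sham-controlled trial in 36 people. It places "participants (n=24) in the experimental group" on active tDCS followed by 60 minutes of arm training. For the rest, "Participants (n=12) in the control group will receive 20 minutes of sham tDCS followed by RAT for 60 minutes". No matching or crossover is described. On outcomes, the section states: "Primary clinical outcome measure is GRASSP prehension performance".

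Section 9 (Data analysis) says that the GRASSP difference in the active arm and "between active vs sham arm (immediately after treatment - baseline) will be analyzed with paired t test", provided a Kolmogorov-Smirnov test supports normality. If it suggests skew, "we will conduct Wilcoxon signed rank test and Wilcoxon rank sum test for these two analyses".

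For the multivariable analysis, "we will fit a mixed model for data collected at baseline and ten sessions and at 30-days follow-up in both study arms". Time is coded 0 at baseline and 1 to 10 for the sessions. On the treatment-by-time term: "The interaction will be added if it will be significant".

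Section 6 (Study Procedures) gives the assessment schedule. The table lists GRASSP at baseline, post-treatment and follow-up, and the text below it says "GRASSP, Grip Strength, SCIM-II and fNIRS measurements will be repeated at post-treatment visit and at 4-week follow-up visit". GRASSP is not listed for treatment sessions 1 to 10.

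The plan names a primary clinical outcome but no primary analysis. It states no alpha, power, effect size or SD.

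**The concern.** The randomized contrast is active tDCS plus training against sham tDCS plus the same training. A paired t test needs each value in one arm to have a partner in the other, and 24 and 12 unrelated patients have none. On the default, normal-data route, the plan therefore names no valid test for its central comparison on the primary clinical outcome. Whoever analyses the data would have to choose a replacement, possibly after seeing them.

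The paired t test that does run is the one within the active arm, and it is listed as an effectiveness analysis. Because both arms receive the same 60 minutes of training, a significant result there can come from training or from retesting alone. Section 10 (Potential Benefits) ties the value of the results to the combined treatment beating training alone, and a within-arm test cannot show that.

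**Working it through.** **Inputs.** Arms of 24 and 12 (Section 4). GRASSP at three visits (Section 6). The documents give no alpha, SD, effect size or correlation, so there is no sample-size figure to reproduce. Assumed throughout: two-sided alpha 0.05, with effects in units of the SD of the GRASSP change score.

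**1. Can the stated test be run?** 24 + 12 = 36, all different people, with unequal arm sizes and no matching. A paired test on the two sets of change scores is undefined. Forcing 12 arbitrary pairs would discard 12 active patients. The noncentrality would be d × √(12/2) with 11 df, against d / √(1/24 + 1/12) = d × √8 with 34 df for a two-sample test. The difference detectable with 80% power would rise from 1.02 to 1.26 SD.

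**2. What does the within-arm paired test show?** Suppose tDCS does nothing and training or retesting moves GRASSP by g SD. The noncentrality is g × √24 with 23 df.

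| Assumed shared gain g | Noncentrality | P(significant), active arm alone | P(significant), valid two-sample test |
|---|---|---|---|
| 0.5 SD | 2.45 | 0.650 | 0.05 |
| 0.8 SD | 3.92 | 0.963 | 0.05 |

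**3. What would a correct two-sample test deliver?** The standard error is √(1/24 + 1/12) = 0.354 SD. Power is 28% at 0.5 SD and 59% at 0.8 SD, and it reaches 80% at 1.02 SD. The 95% CI half-width is t(0.975, 34) × 0.354 = 0.72 SD. With 22 and 11 patients (roughly 10% loss), 80% power needs 1.07 SD.

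**4. Does the mixed model fill the gap?** As written it needs GRASSP at ten sessions, where none is scheduled, and it has no time code for the post-treatment or follow-up visit. Restricted to the three scheduled visits, it was simulated with 20,000 trials per setting. Compound symmetry and an equal effect at both post-baseline visits were assumed. Results were stable for within-patient correlations from 0.5 to 0.9.

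| True effect (SD of change) | Interaction significant, so kept | Interaction dropped |
|---|---|---|
| 0.5 | 28% | 72% |
| 0.8 | 62% | 38% |
| 1.02 | 84% | 16% |

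When the interaction is dropped, the arm term averages the arm difference over all three visits. Its expectation is (0 + d + d)/3 = 2d/3; the simulation gave 0.66 to 0.67. That term also carries between-patient variation. In a separate simulation (4,000 trials per setting, true effect 1.0 SD), its power was 61%, 24% and 13% for correlations of 0.5, 0.8 and 0.9. A two-sample test on change had about 78%.

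**5. What does baseline adjustment add?** With equal baseline and post-treatment variances, the variance of the ANCOVA estimate relative to raw change is (1 − ρ²)(1 + 1/(36 − 4)) / (2(1 − ρ)).

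- ρ = 0.5: 0.75 × 1.03125 / 1.0 = 0.773
- ρ = 0.7: 0.51 × 1.03125 / 0.6 = 0.877
- ρ = 0.9: 0.19 × 1.03125 / 0.2 = 0.980

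Simulation of 60,000 trials gave 0.768, 0.879 and 0.980.

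**The case against.** The strongest reply is that this is a drafting slip. The fallback pairs a signed rank test with a rank sum test for the same two analyses, so the authors clearly knew that one comparison is within patients and the other between groups. Outcome, contrast and time point are fixed, and a paired test on 24 and 12 values would fail visibly rather than mislead quietly. That stands as to intent, and it limits the severity. It does not supply the missing test: the fallback applies only under apparent skew, and Student, Welch and ANCOVA all remain open on the default route.

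Second, the mixed model tests the interaction before deciding whether to keep it, and that is itself a between-arm test. At the three scheduled visits it has about the same power as a two-sample test (28%, 62% and 84% against 28%, 59% and 80%). This is fair. But the plan treats that test as a model-building step and does not declare it the efficacy test. The two-thirds attenuation matters only if the arm term is then read as the effect, which the plan neither says nor rules out.

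Third, the within-arm test is validly paired, and Section 9 does not say it will be taken as evidence for tDCS. The explicit success criteria in Section 4 concern feasibility, and Section 10 states a potential benefit, not a success criterion. These points are correct. The 65% and 96% therefore measure what happens if the within-arm result is read as a tDCS effect. Likewise, the 1.02 SD and ±0.72 SD describe the trial's size, not a cost of the wording.

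Last, ANCOVA is an efficiency gain, not a requirement for validity, and a rank sum test on change is not baseline-adjusted. Both are true, and the fix allows for them.

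**Conclusion.** The concern holds. The only t test in the plan is assigned to a comparison to which it cannot be applied; the mixed model as written relies on GRASSP measurements that are not scheduled; and no between-arm analysis is designated primary. That conclusion follows from the text alone and needs no assumption.

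The sizes do rest on assumptions: alpha, effect sizes, shared gain and correlations, none of which the documents give. Under them, a within-arm result read as a tDCS effect would mislead in about 65% to 96% of trials with no tDCS effect. Even the correct comparison would be imprecise, which is why the estimate and its interval matter more than a p-value. This should be fixed before analysis. It does not threaten the feasibility aim or the conduct of the trial.

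**What to change.** In Section 9:

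- Replace the paired t test for active versus sham with an ANCOVA of post-treatment GRASSP prehension performance on arm, adjusted for its baseline value. Report the adjusted difference with a 95% CI. At minimum, specify a Welch two-sample t test on change.
- State that this is the primary between-arm effectiveness analysis.
- Keep the Wilcoxon rank sum test on change as the non-parametric counterpart. Say in advance that it is reported as a sensitivity analysis, so that the normality test does not choose the primary result.
- Report within-arm changes descriptively in both arms, not as evidence for tDCS.
- If the mixed model is kept as supportive, fit it to baseline, post-treatment and follow-up, the visits at which GRASSP is scheduled, and always include the arm-by-time term.

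The cost is a few sentences. No new data or visits are needed.

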Treatment at home (Duration: two hours): Home-treatment sessions will start on the following week (Monday through Friday) and continue for two-weeks (total 10 treatment sessions). During each treatment session primary motor cortex (C3 or C4 according to international EEG system) will be stimulated with anodal tDCS at 2mA for 20 minutes. Electrode sizes are 5x7cm, saline-soaked. Active (anodal) electrode will be placed over the primary motor cortex and reference electrode will be placed over contralateral supraorbital area. This single-position headgear include clearly labeled sponge markers to eliminate room for user error (see attached brochure for tDCS with head gear and sponge electrodes). Participants in the sham stimulation (control) group will use same stimulation location, however the duration of stimulation will be set to 30 seconds at the beginning and end of 20 minutes. This is a reliable method of sham stimulation as sensations arising from tDCS treatment occur only at the beginning of application (Gandiga, Hummel et al. 2006). Subjects often feel during current ramp up; however the same procedure will be adopted for sham stimulation (that will receive active current for 30 seconds only (insufficient time to produce meaningful changes) and therefore mimic the initial sensation associated with active stimulation. It should be noted that less than 3 minutes of tDCS induces no effects on cortical excitability (Nitsche and Paulus 2000) and also using 30 seconds of sham is a reliable method of blinding as shown by a randomized controlled study (Gandiga, Hummel et al. 2006).

Immediately after stimulation ceases, participants will continue with unilateral repetitive arm and finger exercises for 60 minutes. Exercise difficulty will gradually increase and adjusted as needed per participants tolerance. All treatment sessions will be supervised in real-time via videoconferencing by [name] in her office at the NeuroRecovery Research Center at TIRR/Memorial Hermann.

The tDCS device in this study (Soterix 1x1 tdCS mini-CT stimulator, see attachment), is specifically designed and developed for home-use. The intensity and duration of stimulation will be pre-programmed by [name]. After pre-programming device, it won't allow patient/caregiver to make changes. All session will be monitored remotely by [name]. After home-therapy ends, study participant will bring the FitMi and Music Glove devices, and the laptop back to the research lab.

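### The mixed model in Section 9 is built on ten session times and favours a cubic, but GRASSP is scheduled at only three visits and the follow-up has no time code

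*Combined protocol and SAP*

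**What the plan says.** Section 9 (Data analysis) describes the multivariable analysis as follows: "we will fit a mixed model for data collected at baseline and ten sessions and at 30-days follow-up in both study arms". Its fixed effects are treatment arm and "time (0 for baseline, 1-10 for ten sessions". Time is first nominal, with a test of arm by time, and "The interaction will be added if it will be significant". Time is then to be modelled parametrically: "The mean trajectory plot will guide us on the parametric form of time", and "Our emphasis will be linear time and 3rd-order polynomial time". The reason for preferring the cubic is: "We tend to favor the 3rd-order polynomial time as we believe that the GRASSP score will increase greatly for the first few sessions". The next paragraph adds a random time slope and several serial correlation patterns, with AIC to guide the choice.

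The assessment schedule is different. Section 4 (Study Design), on the clinical outcomes, says: "Assessments will be repeated immediately after completion of 10 sessions and at 4-weeks follow-up". The Schedule of activities in Section 6 marks GRASSP at baseline, post-treatment (Day 5±3) and follow-up (Day 35±5), with nothing under the treatment sessions. The text below the table names the same two repeat visits. Section 7 places all assessments at the research centre, whereas the ten sessions take place at home.

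**The concern.** The model's time variable does not describe the data it will receive. GRASSP prehension performance is the primary clinical outcome, and its simple comparison in Section 9 uses only the change from baseline to immediately after treatment. Whether any benefit lasts to follow-up is therefore examined only in this mixed model. If the model cannot be run as specified, the analyst must devise a time code and a functional form. Because the plan lets a plot of the means guide the form, that could happen after the data have been seen.

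A second matter sits in the same paragraph. In a randomised comparison with baseline among the modelled responses, the arm-by-time term carries the arm difference in change. Dropping it when it is not significant leaves an arm main effect that averages over baseline, where the expected difference is zero.

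**Working it through.** The plan states no power or precision figure on this point, so there is none to reproduce.

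**Inputs.** 24 active and 12 sham participants (Section 4). GRASSP at 3 visits (Sections 4 and 6). Model occasions: baseline, 10 sessions and follow-up, which makes 12 (Section 9).

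**1. Occasions.** Scheduled GRASSP values: 36 × 3 = 108. Implied by the model text: 36 × 12 = 432. Of the 11 codes given (0 to 10), one holds GRASSP data, or two if post-treatment is read as time 10, which the plan does not say. Follow-up is among the model's data but has no code.

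**2. Estimability on a common three-visit code.** Three distinct times support at most three time coefficients per arm, so at most six with a full arm interaction. The ranks below were computed for the codes (0, 10, 11), (0, 1, 2) and (0, 17, 47), with the same result each time.

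| Form of time | Rank / columns | With arm interaction |
|---|---|---|
| Linear | 2 / 2 | 4 / 4 |
| Quadratic | 3 / 3 | 6 / 6 |
| Cubic | 3 / 4 | 6 / 8 |
| Nominal, three visits | 3 / 3 | 6 / 6 |

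For example, t(t − 10)(t − 11) is zero at 0, 10 and 11. Any multiple of it can be added to a fitted cubic without changing the fit.

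**3. Actual visit days.** Assumed axis: session 1 on Day 1, session 10 on Day 12, later windows counted from the last session. Baseline then falls on Day −6 to 0, post-treatment on 12 + (2 to 8) and follow-up on 12 + (30 to 40). With days drawn uniformly in these windows, the cubic with arm interaction had rank 8 of 8 in all 2,000 simulated designs. It is therefore estimable, but only through scatter within windows, and no GRASSP value falls between Day 1 and Day 12. Suppose one course of recovery is complete by session 3 and another rises steadily to session 10, with the same total gain. Both give the same values at the three visits, so no fit can tell them apart.

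**4. Do the printed days supply a code?** Section 6 says "Home-treatment sessions will start on the following week (Monday through Friday) and continue for two-weeks (total 10 treatment sessions", which spans 5 + 2 + 5 = 12 calendar days. Baseline ending on Day 0 and post-treatment on Day 5±3 therefore cannot share an origin. Section 6 places the post-treatment visit within a week of completion, so Day 5±3 can be read from the end of treatment. From post-treatment to follow-up is 35 − 5 = 30 days, with a window range of 30 − 8 = 22 to 40 − 2 = 38 days, which also contains 28 days (4 weeks). No origin is stated for follow-up.

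**5. Dropping the interaction.** Let the arm differences at the three visits be 0, d1 and d2. With nominal visits, complete data and no interaction, the arm term is a weighted mean of these, with weights proportional to the row sums of the inverse covariance matrix.

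- Random intercept: weights 1/3, 1/3, 1/3.
- AR(1) with correlation ρ between adjacent visits: weights 1/(3 − ρ), (1 − ρ)/(3 − ρ), 1/(3 − ρ). For ρ = 0.5 these are 0.40, 0.20, 0.40. For ρ = 0.8 they are 0.45, 0.09, 0.45.

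| Covariance (assumed) | Share of d1 returned if d2 = 0 | If d2 = d1 |
|---|---|---|
| Random intercept | 33% | 67% |
| AR(1), ρ = 0.5 | 20% | 60% |
| AR(1), ρ = 0.8 | 9% | 55% |

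Under all three structures the term would return the whole of d1 only if the effect doubled by follow-up (d2 = 2d1). For the random intercept, for example, (0 + 1 + 2)/3 = 1.

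**The case against.** The strongest reply is that little depends on this. Feasibility is the first aim and is analysed descriptively. The baseline to post-treatment GRASSP comparison does not use the mixed model. The polynomial is worded tentatively, and the plan's first step, nominal time with an interaction test, works on three visits because software would use only the levels observed. All of that stands and limits the consequence. It does not supply a code for follow-up, or a use for the form the plan prefers.

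It can also be said that the model may be meant for another outcome. The sentence names none, so GRASSP is an inference. But the only reason given for the cubic is about GRASSP. The pain, fatigue and tDCS side-effect measures taken at sessions 1-10 are not marked at baseline or follow-up, so they do not fit the described structure either. Nor can the mismatch be put down to a damaged table, since the prose in Sections 4 and 6 agrees with it.

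A reader might infer three stronger things that the documents do not support:

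- **That the mixed model cannot be fitted at all, or that the cubic fails under every coding.** Nominal, linear and quadratic time are estimable on three visits, and the cubic becomes formally estimable with actual days.
- **That 4 weeks, 30 days and Day 35±5 contradict each other.** They agree if counted from the post-treatment visit. What is missing is the origin.
- **That dropping the interaction leaves a fixed one third to two thirds of the effect.** That holds only under a random intercept. Section 9 also considers serial correlation and a random slope, and the share changes with the covariance.

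**Conclusion.** The point holds and should be fixed. As written, the time variable and the favoured cubic cannot be applied to the scheduled GRASSP data. Ten session codes are empty (nine if post-treatment is taken as time 10), follow-up is uncoded, and the cubic is one coefficient short on a common three-visit code, or two short with arm interaction. Actual days would not recover the early rise for which the cubic was chosen. Confidence in this part is high. It rests on the schedule, and on reading GRASSP as the modelled outcome.

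The interaction rule is a related weakness, and its size is less certain. If the term is left out as non-significant and the effect does not grow after treatment, the arm main effect understates the post-treatment arm difference. The share returned runs from 9% to 67% over the covariances and degrees of persistence assumed here. The direction is firm under those structures, but the percentages are illustrations.

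The damage is confined to the longitudinal analysis, chiefly to follow-up GRASSP, which no other planned analysis covers.

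**What to change.** In Section 9, for this model:

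1. Name GRASSP as the outcome.
2. Replace the session coding and the cubic step with a three-level visit factor (baseline, post-treatment, follow-up).
3. Keep the arm-by-visit term whatever its significance.
4. Prespecify the arm contrasts at post-treatment and at follow-up.
5. State one follow-up timing with its origin.
6. Revise the covariance paragraph to match. A random time slope and exponential correlation need numeric times, which a visit factor does not supply. On three visits a random intercept added to an unrestricted Toeplitz is redundant, because the Toeplitz already contains a common covariance. Either prespecify one structure suited to three visits (for example, unstructured) and remove the random slope and the list of serial patterns for GRASSP, or define the numeric visit times they need.

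If GRASSP at each session is really intended, reconcile the Schedule of activities and the assessment text with Section 9 instead.

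The cost is a rewrite of the two mixed-model paragraphs, with no new visits or data. Always keeping arm-by-visit uses two more coefficients, with up to 108 observations. What is given up is a within-treatment GRASSP trajectory that the schedule does not measure.
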